2.2 Secondary objectives

Key Secondary Objectives

- To evaluate everolimus with reduced exposure CNI compared to MPA plus standard exposure CNI at 12 months post-transplantation with respect to the composite efficacy failure rate of (treated biopsy proven acute rejection (tBPAR), graft loss or death).
- To evaluate the binary composite endpoint of tBPAR or eGFR < 50 mL/min/1.73m² (MDRD4) Month 12 among compliant subjects.

Other Secondary Objectives

To evaluate, by treatment group;

- The incidence of composite endpoint of tBPAR or eGFR < 50 mL/min/1.73m² (MDRD4) at Month 24.
- The incidence of composite endpoint of tBPAR (excluding Banff grade 1A acute rejections) or eGFR < 50 mL/min/1.73m² (MDRD4) at Month 24.
- The incidence of composite endpoint of tBPAR or eGFR < 50 mL/min/1.73m² (MDRD4) at Month 12 by subgroup (see Section 9.4.4).

- The incidence of composite endpoint of tBPAR, graft loss or death at Month 24.
- The incidence of composite endpoint of tBPAR, graft loss, death, or loss to follow-up at Months 12 and 24.
- The incidence of composite endpoint of tBPAR, graft loss, death or eGFR < 50 mL/min/1.73m² at Months 12 and 24.
- The incidence of composite endpoint of graft loss or death at Month 12 and 24.
- The incidence of individual endpoints of death, graft loss, tBPAR, BPAR, tAR, AR and humoral rejection at Months 12 and 24.
- The incidence of tBPAR by severity and time to event.
- The incidence of tBPAR excluding Banff 1A grade acute rejections
- The incidence of transplant recipients with eGFR < 50 mL/min/1.73m² at Months 12 and 24.
- Renal allograft function and change in renal allograft function from Month 1 (eGFR) at Months 12 and 24.
- The evolution of renal function, as eGFR, over time by slope analysis.
- Renal function by Cystatin C-based and other alternate formulae (e.g. CKD-EPI).
- The incidence of adverse events, serious adverse events and adverse events leading to study regimen discontinuation.
- The incidence of CMV and BKV, new onset diabetes mellitus, chronic kidney disease with associated proteinuria and CNI associated adverse events.
- Urinary protein and albumin excretion by treatment estimated by urinary protein/creatinine and urinary albumin/creatinine ratios.
- The incidence of major cardiovascular events.
- The incidence of malignancies.

3 Investigational plan

[figure not shown]

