3.1 Study design

This is a 2-year, randomized, multicenter, open-label, 2-arm study evaluating graft function with everolimus and reduced CNI versus MPA and standard CNI in adult *de novo* renal transplant recipients (Figure 3-1). Consented subjects will enter the screening period and upon

Protocol No. CRAD001A2433

meeting eligibility criteria, including successful transplantation, will enter the initial 12 Month treatment period then continue in the next treatment period to Month 24.

Figure 3-1 Study design- Primary Treatment to M12, Extension to M24

Upon meeting eligibility criteria, approximately 2040 subjects (around 1020 per treatment arm) will be randomized (1:1) within 24 hr of transplantation, to the following treatment groups:

Group 1: Everolimus plus Reduced CNI (see Table 5-1 for CNI target trough levels)

Group 2: MPA plus Standard CNI (see Table 5-1 for CNI target trough levels)

Randomization will be stratified, within treatment groups, to balance; 1) recipients by donor type, living donors (LD), deceased standard criteria donors (SCD) and deceased expanded criteria donors ECD); 2) CNI usage, cyclosporine vs tacrolimus. The overall study population will contain no less than 50% recipients of living donor transplants and subjects taking cyclosporine will comprise no more than 20% of the population.

Subjects will commence the randomized study regimen within 24 hr post-reperfusion of the allograft and should continue on the assigned open-label study regimen until the Month 24 visit.

Induction therapy, with Basiliximab or rATG only, is mandatory for all subjects starting pre-or peri-operatively on the day of kidney transplant surgery (For details see Section 5.5.4). Corticosteroids are mandatory for all subjects through Month 24 and can be administered according to local practice but with a minimal daily dose of 5 mg prednisone, or equivalent. The study regimen/medication definition comprises either a) everolimus plus reduced CNI OR b) MPA plus standard CNI. Cyclosporine and tacrolimus dose adjustments will be made according to local trough values in order to maintain timely adherence to the protocol-specified ranges (See Table 5-1). Subjects are expected to remain on the original CNI (combined with everolimus or MPA) to which they were randomized until at least Month 24. However, if subjects discontinue either CNI due to AE/tolerability and can maintain everolimus or MPA

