5.5.9 Discontinuation of study treatment and discontinuation from study

Discontinuation of study regimen

The Dosage administration records for everolimus, MPA, tacrolimus and cyclosporine will be used to record if a subject has permanently discontinued study treatment and why.

Possible reasons for study treatment discontinuation are:

- Adverse Event
- Lack of Efficacy
- Technical problems
- Subject/Guardian Decision
- Lost to follow-up
- Death
- Graft Loss

The investigator should discontinue a subject from their randomized treatment regimen if, on balance, he/she believes that continuation would be detrimental to the subject's well-being.

If, at any time throughout the study, the randomized treatment regimen or any component of the regimen is interrupted for longer than 21 consecutive days, unless being held due to an elective surgical procedure then study regimen should be discontinued.

Subjects who become pregnant while taking study medication must be discontinued from study medication and from the study, such pregnancies should be reported as SAEs to Novartis DSE and entered as AEs in the CRF, the reason for discontinuation of study medication should be recorded as AE and reason for discontinuation from study is pregnancy (see next section below).

Subjects who discontinue their randomized study regimen (any component whether everolimus, MPA or the CNI) should remain in the study, if possible, and receive standard of care immunosuppression, according to local practice, until completing the study at Month 24. Visits and assessments for such subjects are described in Table 6-1. All immunosuppressants after

discontinuation of study regimen must be recorded on the Concomitant Medication CRF under the Immunosuppressive category.

Subjects are expected to remain on the original CNI (combined with everolimus or MPA) to which they were randomized until at least Month 24. However, if subjects discontinue either CNI due to AE/tolerability and maintain everolimus or MPA combined with the alternate CNI, administered to respective target levels per protocol, they will not be considered to have discontinued study regimen/medication.

Discontinuation from Study and Study/Period completion

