Vital signs variables include measurements of oral body temperature, systolic and diastolic blood pressures, pulse and body weight. Vital signs will be examined for abnormal values and change from baseline according to pre-specified clinically notable criteria. Appropriate incidence rates of clinically notable abnormalities will be provided. Further, descriptive statistics of all vital signs variables as well as the changes from baseline will be presented by visit. A by-subject listing of all vital signs (with clinically notable abnormalities being flagged) will be generated.

Laboratory data

Descriptive statistics (mean, standard deviation, minimum, median and maximum) of quantitative laboratory variables, including change from Baseline, will be generated by visit for laboratory parameters. Categorical levels of urinary protein/creatinine ratio (<30, 30 - <500, 500 - 1000, 1000 - 3000, = 3000 mg/g) will additionally summarized by visit.

Abnormalities according to the clinical notable criteria (see Appendix 1) will be identified and tabulated for each applicable lab parameter. Lipids levels are categorized based on the following criteria per American Heart Association (Adult treatment panel III 2002). A by-subject listing of individual subject laboratory data will be generated; values outside of clinical notable will be flagged.

Protocol No. CRAD001A2433

Amended Protocol Version v01 Clean

- Triglycerides
 - Normal: < 150 mg/dL
 - Borderline high: 150 <200 mg/dL
 - High: 200 <500 mg/dL
 - Very high: $\geq 500 \text{ mg/dL}$
- Total cholesterol
 - Normal: < 200 mg/dL
 - Borderline high: 200 <240 mg/dL
 - High: \geq 240 mg/dL
- HDL cholesterol
 - Low: < 40 mg/dL for men, <50 mg/dL for women
 - Normal: 40 60 mg/dL for men, 50 60 mg/dL for women
 - Optimal: ≥60 mg/dL
- LDL cholesterol
 - Optimal: < 100 mg/dL
 - Near or above optimal: 100 <130 mg/dL
 - Borderline high: 130 <160 mg/dL
 - High: 160 <190 mg/dL
 - Very high: ≥ 190 mg/dL

Total cholesterol /HDL ratio level is defined as

- Normal: <5
- High: >=5 but <=7
- Very High: >7

Tolerability

Tolerability of the regimens is assessed by summarizing the percentage of subjects requiring dose adjustment or interruption and premature treatment discontinuations due to adverse events by treatment group.

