## 2.3 Patient Disposition, Demographics and Baseline Characteristics

### 2.3.1 Patient Disposition

Patient disposition will be summarized in terms of the number and percentage of patients who complete the screening, prematurely discontinued from study medication and from study (by primary reasons). When there are multiple reasons for discontinuation associated to study drugs and CNI that happened the same day, the primary reason will be the one related to, by order of priority, Everolimus, Tacrolimus, MPA and Cyclosporine. The number of patients in the different analysis sets, incidence of protocol deviations, and incidence of major protocol deviations and other deviation criteria leading to exclusion from per-protocol set will be summarized by treatment group. Listings of screen failure and study completion with primary reasons for premature discontinuation of the randomized study treatment will also be provided.

In addition, the following listings will be presented:

- Screen failure
- Study completion status
- Protocol Deviations (PDs)
- Major protocol deviations and other deviation criteria leading to exclusion from per-protocol set
- Patients excluded from any analysis sets

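### For tacrolimus patients, the SAP's tie-break for same-day stops takes the primary reason from everolimus in one arm but from tacrolimus, not MPA, in the other

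*SAP*

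**What the plan says.** SAP 2.3.1 summarises patients who "prematurely discontinued from study medication and from study (by primary reasons"), and adds a listing with primary reasons for stopping randomised treatment. Its tie-break starts "When there are multiple reasons for discontinuation associated to study drugs and CNI that happened the same day" and then states that "the primary reason will be the one related to, by order of priority, Everolimus, Tacrolimus, MPA and Cyclosporine". No rationale is given. The SAP document history dates the addition of the hierarchy to 27 February 2018.

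Two protocol passages explain why a tie can arise. Protocol 3.1 defines a two-drug regimen in each arm: "The study regimen/medication definition comprises either a) everolimus plus reduced CNI OR b) MPA plus standard CNI". Protocol 5.5.9 says that the separate dosage records for everolimus, MPA, tacrolimus and cyclosporine are "used to record if a subject has permanently discontinued study treatment and why". The permitted reasons include adverse event, lack of efficacy and subject decision. Two drugs stopped on one day can therefore carry different reasons.

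**The concern.** A patient in either arm takes one partner drug (everolimus or MPA) and one CNI. A neutral tie-break would pick the same class of drug in both arms. The SAP list does not, because tacrolimus sits below everolimus but above MPA.

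Take a tacrolimus patient who stops the partner drug for an adverse event and stops tacrolimus on the same day by own decision. In the everolimus arm the table shows an adverse event. In the MPA arm it shows subject decision. In this open-label trial, readers will compare reasons for stopping treatment between arms, and part of any difference in that table could come from the labelling rule rather than from the patients.

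**Working it through.** The plan states no figure to reproduce, so the check has two parts: apply the rule, then see what it could do under stated assumptions.

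**Step 1. Apply the order to each arm and CNI.**

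| Arm | CNI | Drug supplying the reason | Class |
|---|---|---|---|
| Everolimus | Tacrolimus | Everolimus | Partner |
| Everolimus | Cyclosporine | Everolimus | Partner |
| MPA | Tacrolimus | Tacrolimus | CNI |
| MPA | Cyclosporine | MPA | Partner |

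The arms differ for tacrolimus patients only. For cyclosporine patients the partner drug supplies the reason in both arms.

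**Step 2. Inputs.**
- From SAP section 3: 1,020 patients per arm; 80% tacrolimus, 20% cyclosporine (planning values).
- Assumed: each discordant same-day stop pairs one adverse-event reason with one other reason. Let q be the share of these in which the partner drug carries the adverse event; in the rest the CNI carries it. Take q as equal in both arms and for both CNIs, and take such stops as equally frequent with either CNI.
- Assumed: a fraction d of each arm has such a stop. The documents give neither q nor d.

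**Step 3. Share of discordant stops labelled as adverse event.**
- Everolimus arm: q
- MPA arm: 0.8(1 − q) + 0.2q = 0.8 − 0.6q
- Artificial difference, everolimus minus MPA: q − (0.8 − 0.6q) = 1.6q − 0.8

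| q | Everolimus | MPA | Difference |
|---|---|---|---|
| 0.1 | 10% | 74% | −64 points |
| 0.4 | 40% | 56% | −16 points |
| 0.5 | 50% | 50% | 0 |
| 0.6 | 60% | 44% | +16 points |
| 0.9 | 90% | 26% | +64 points |

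The difference vanishes at q = 0.5 and changes sign below it.

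**Step 4. Convert to patients: 1,020 × d × (1.6q − 0.8).**

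| d | Discordant stops per arm | q = 0.6 | q = 0.9 |
|---|---|---|---|
| 0.5% | 5.1 | 0.8 patients (0.08 points) | 3.3 patients (0.32 points) |
| 1% | 10.2 | 1.6 patients (0.16 points) | 6.5 patients (0.64 points) |
| 5% | 51 | 8.2 patients (0.8 points) | 32.6 patients (3.2 points) |

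For q = 0.4 and q = 0.1 the same figures apply with the sign reversed.

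**Step 5. Repeat with a mirrored order.** If everolimus and MPA share the first rank and the two CNIs share the second, both arms report q, and the difference is zero for every q and d.

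**The case against.** The strongest reply is that this is a tie-break for a descriptive table. It does not change who counts as having stopped treatment, the date of last dose (SAP 2.1.1.2), the analysis sets (SAP 2.2), or the primary and key secondary endpoints (SAP 2.5.1 and 2.6.1). No hypothesis test uses it. Several permitted reasons, such as death, graft loss or loss to follow-up, describe the patient rather than one drug, so discordant pairs are probably uncommon. All of this stands, and it is why the point ranks low. It does not explain the order. SAP 2.1.1.2 calls it conservative to date the everolimus regimen by everolimus alone, which might support ranking everolimus first, but that does not justify placing tacrolimus above MPA and cyclosporine below it.

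Three stronger readings are tempting, and the documents do not support them.

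- **That the order contradicts Protocol 5.5.9.** A reader might infer this from the CNI-switch rule, under which patients who change CNI are such that "they will not be considered to have discontinued study regimen/medication". That exception requires everolimus or MPA to be maintained with the other CNI. The same section counts stopping any component, the CNI included, as stopping the regimen. If the partner drug stops on the same day, the exception cannot apply.
- **That the rule favours one arm.** Step 3 shows that the sign depends on q, which is not given.
- **That the adverse-event objective is distorted.** Protocol 2.2 lists "The incidence of adverse events, serious adverse events and adverse events leading to study regimen discontinuation", and Protocol 9.5.3 lists "premature treatment discontinuations due to adverse events by treatment group" under tolerability. SAP 2.8.1 has its own table of events leading to premature discontinuation of study drug, and Protocol 7.1 has the action taken on study treatment recorded with each adverse event. No text applies the hierarchy to these outputs.

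**Conclusion.** The asymmetry is real and follows directly from the stated order. For tacrolimus patients with discordant same-day stops, the same records are labelled by the partner drug in the everolimus arm and by the CNI in the MPA arm. The consequence is confined to the disposition summary and listing by primary reason. Its size and direction are unknown. The illustrative counts above rest on assumed values of d and q, on equal q in both arms, and on exactly one adverse-event reason per discordant pair. At the lower frequencies shown (d of 0.5% to 1%), the net effect on the adverse-event category is a handful of patients per arm or fewer. This is a low-priority reporting correction and does not bear on the trial's inferential results.

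**What to change.** In SAP 2.3.1, replace the four-drug list by one class order for both arms: the reason recorded for everolimus or MPA first, then the reason recorded for tacrolimus or cyclosporine. Alternatively, drop the hierarchy and tabulate the reasons for each drug separately by arm. If the present order is kept, state its rationale and report by arm how many patients had their primary reason settled by it. The cost is one sentence in the SAP and a re-run of the disposition table and listing. The reasons are already recorded per drug, so no new data are needed.

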### 2.3.2 Patient Demographics and Baseline Characteristics

Demographic and background information will be summarized based on the FAS population.

Incidence rates of diabetes at baseline (see the definition in [Section 2.8.3.3](#)) and delayed graft function will be also summarized.

Delayed graft function is defined when any of the following criteria are met within 21 days (end day of Week 2 visit window) after transplant:

- AE eCRF page: MedDRA lower level term includes words: “graft dysfunction” or “graft function delayed”; verbatim contains “delayed graft function” or “DGF”.
- Kidney Allograft Rejection eCRF page: “Primary reason rejection was suspected” = Delayed or slow recovery of graft function post-revascularization” or “Primary clinical diagnosis” = “delayed graft function”.

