In case of DGF, treatment will be according to local practice, but the randomized study regimen cannot be interrupted for more than 21 consecutive days. DGF treatments must maintain sufficient immunological coverage for the graft and may include maintaining, interrupting or reducing the dose of CNI and the use of anti-thymocyte globulin. In case of use of depleting antibody hematological parameters (e.g. lymphocytes, WBC and platelets) must be monitored carefully. Use of MPA and everolimus in subjects randomized to the other treatment arm (i.e. everolimus or MPA respectively) is prohibited during any interruption whether for DGF or other reasons

If a subject with DGF is not able to return to or maintain their randomized study regimen as per protocol after 21 consecutive days of interruption, the subject should be discontinued from the study. If a subject is placed on permanent dialysis (or retransplanted) the Graft Loss, and Adverse Event CRFs should be completed, as well as an SAE report of Graft Loss submitted. Dialysis treatments should be recorded on the Dialysis CRF. Retransplantation should be recorded on the surgical and medical procedures CRF.

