### 2.2.1 Subgroup of Interest

The following demographic/baseline characteristics are defined at the study level as subgroups for specified analyses:

- Recipient characteristics:
  - Age group: <60 vs ≥60 yr
  - Gender
  - Race: Caucasian, Black, Asian and All other races
  - Region: US, EU, Asia, Australia, Latin America, and Middle East

- DGF (delayed graft function)
- BMI <30 and  $\geq 30$
- Donor/transplant characteristics:
  - Age group: <60 vs  $\geq 60$  yr
  - Gender
  - Cold ischemia time: < 20 vs  $\geq 20$  hr
  - End stage disease leading to transplant (Glomerular disease, Diabetes mellitus and All other diseases)
  - Donor type (living donor, standard criteria and expanded criteria deceased donor): donor type will be derived based on Kidney Donor Background Information eCRF, and not the randomization stratification from IRT.
  - HLA mismatches:  $\leq 3$  vs  $> 3$
- CNI (tacrolimus vs. cyclosporine)
- Induction (basiliximab vs. rATG):
  - Basiliximab: preferred term: BASILIXIMAB; drug code/ID: 10892631
  - rATG: preferred term: ANTITHYMOCYTE IMMUNOGLOBULIN, or ANTITHYMOCYTE IMMUNOGLOBULIN (RABBIT); drug code/ID: 10878131 or 10878151

As early use of rATG can be for delayed graft function, type of induction will be identified as the first intake of rATG or basiliximab by Day 1 post-transplant.

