## 4.2 Missing Data Handling

### 4.2.1 Missing GFR Data Imputation

#### 4.2.1.1 Main Imputation

The following is the main imputation method for handling missing eGFR data at Month 12. A similar imputation rule can be applied for missing eGFR at Month 24. These imputations will be applied to the primary analyses for the composite endpoint of tBPAR or eGFR < 50 mL/min/1.73m^2, as well as for eGFR alone. For the component of eGFR < 50 mL/min/1.73m^2, a value for missing eGFR as a continuous variable will be imputed first, then it will be dichotomized in order to derive this endpoint.

- Under the assumption of missing not at random (MNAR), patients who lost their grafts will be assigned a value of zero for their missing eGFR at the visits on and after graft loss;
- Multiple imputation: Otherwise, under the assumption of missing at random (MAR), patients who had missing values including those who died with a functioning graft will have a 12-month eGFR imputed using multiple imputation method based on the covariates/factors CNI, region, donor type, HLA mismatch ( $\leq 3$  vs  $> 3$ ), induction therapy, recipient gender, recipient age, donor age, and DGF, and all eGFR (MDRD4) data collected at the visit windows during the analysis period of interest. In the multiple imputation, recipient age, donor age and eGFR (MDRD4) data will be treated as continuous variables. To help preserve the relationship between outcome and covariates within each treatment, a separate model will be run for each treatment. This will also help ensure that the imputation model does not make stronger assumptions on data relations than the analysis model.

To ensure that results can be replicated, the data should be sorted by patient number before running the model (the data should be in horizontal format with one row per patient). If there are multiple renal function assessments within a visit window, guidelines given in [Section 2.1](#) will be followed, i.e., the closest value to the planned visit (midpoint of visit window for post-baseline visits) will be taken (if tie, the last will be used) for imputation. In addition, the seed used in the multiple imputation will be 2433.

See dummy SAS codes below.

```
proc mi data=DATAIN out=DATAOUT nimpute=100 seed=2433;
  by treatment;
  class CNI region donor HLA induction gender_r DGF;
```

```
fcs reg (/details);  
var CNI region donor HLA induction gender_r age_r age_d DGF GFR_vis1  
GFR_VIS2 ... GFR_VISm;  
run;

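### DGF is taken from adverse-event wording and the rejection form, one trigger can share an episode with tBPAR, and a mostly post-randomization flag is listed as baseline

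*SAP*

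**What the plan says.** **Definition.** SAP 2.3.2: "Delayed graft function is defined when any of the following criteria are met within 21 days" after transplant. There are two sources:

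- The adverse-event form: "AE eCRF page: MedDRA lower level term includes words" for graft dysfunction or delayed graft function, or verbatim text naming DGF.
- The Kidney Allograft Rejection eCRF: either "Primary reason rejection was suspected" is answered with "Delayed or slow recovery of graft function post-revascularization", or the primary clinical diagnosis is delayed graft function.

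Dialysis appears in neither source. Protocol 5.5.5, in its part on treating DGF, says: "Dialysis treatments should be recorded on the Dialysis CRF". Table 6-1 also schedules a dialysis log as needed. The protocol uses the term DGF without defining it.

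**Status.** SAP 2.2.1 lists DGF under this sentence: "The following demographic/baseline characteristics are defined at the study level as subgroups for specified analyses". SAP 2.1.1.4 defines a baseline value as the last one before randomization.

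**Uses.**

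- Subgroup for the primary endpoint (SAP 2.5.4.3), the key secondary endpoint (2.6.4), eGFR < 50 at Month 12 (2.7.2.1) and tBPAR at Month 12 (2.7.2.2).
- Covariate in the logistic model that decides whether the two CNIs are pooled (2.5.2), and in the eGFR ANCOVA and mixed model (2.7.3.2).
- Covariate in the main imputation (4.2.1.1: "recipient gender, recipient age, donor age, and DGF") and in the control-based imputation (4.2.1.2).

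DGF is absent from the protocol's imputation covariates (9.4.3), subgroup list (9.4.4) and ANCOVA covariates (9.5.2). The SAP added it.

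**The concern.** A variable used as a baseline subgroup and covariate should be fixed before treatment can influence it, and should not be built from the outcome. DGF as derived here meets neither condition. It depends on how investigators who know the arm word an early event. One of its triggers sits on the form that also feeds tBPAR, so a single early episode can place a patient in the DGF subgroup and also be that patient's primary-endpoint event.

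At stake are the DGF subgroup results, the DGF rates shown beside the baseline data, the pooling decision and the adjusted eGFR comparisons. The SAP shows awareness of the timing problem in a related variable. In 2.2.1 it fixes induction type by the first agent given by Day 1, because early rATG may be given for DGF. DGF itself has no such protection.

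**Working it through.** No figure in either document depends on this definition, so there is nothing to reproduce. The check is a comparison of the text, followed by two illustrations with assumed inputs.

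**1. Can one episode set both flags?** BPAR (SAP 4.3.4) needs a primary clinical diagnosis of acute, or acute and chronic, rejection plus a positive biopsy entry. tBPAR (4.3.5) adds that anti-rejection therapy was given.

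| Entry on the rejection form within 21 days | DGF? | Can the same episode be tBPAR? |
|---|---|---|
| Reason suspected = slow recovery; diagnosis = acute rejection; biopsy positive; treated | Yes | Yes |
| Reason suspected = slow recovery; diagnosis not acute rejection | Yes | No |
| Diagnosis = delayed graft function | Yes | No, the BPAR diagnosis condition fails |

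Only the reason-suspected trigger overlaps with the outcome.

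**2. Is it a baseline variable?** Randomization is within 24 hr of completing surgery (Protocol 4.1) and the DGF window runs 21 days from transplant. About 21 − 1 = 20 days therefore fall after randomization, in an open-label study (Protocol 5.4). By SAP 2.1.1.4 this is not baseline.

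**3. Illustration of the overlap (all inputs assumed).** Let tBPAR be 10% in patients flagged by other routes and 50% in those flagged only through the reason-suspected trigger. Let s be the share of the flagged group in the second category.

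Flagged tBPAR rate = (1 − s) × 10% + s × 50% = 10% + 40s points.

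With 20 of 200 flagged this way (s = 10%): (180 × 0.10 + 20 × 0.50) / 200 = 28/200 = 14%. With s = 0 it is 10%. If this is equal in both arms, it changes what the subgroup is but does not bias the treatment contrast.

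**4. Illustration of arm-dependent labelling (all inputs assumed).** No true treatment effect; overall event rate 50%; 70% in true DGF; true DGF prevalence 20%. The event rate without DGF is (0.50 − 0.20 × 0.70) / 0.80 = 0.45.

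- *Over-labelling differs by arm:* sensitivity 0.8 in both, specificity 0.90 (EVR) and 0.98 (MPA).
  - EVR, flagged DGF: (0.16 × 0.70 + 0.08 × 0.45) / 0.24 = 0.148/0.24 = 61.7%.
  - MPA, flagged DGF: (0.16 × 0.70 + 0.016 × 0.45) / 0.176 = 0.1192/0.176 = 67.7%.
  - Spurious difference: −6.1 points (from unrounded rates).
- *Under-labelling differs by arm:* specificity 1 in both, sensitivity 0.5 (EVR) and 0.9 (MPA).
  - EVR, no DGF: (0.10 × 0.70 + 0.80 × 0.45) / 0.90 = 0.43/0.90 = 47.8%.
  - MPA, no DGF: (0.02 × 0.70 + 0.80 × 0.45) / 0.82 = 0.374/0.82 = 45.6%.
  - Spurious difference: +2.2 points.

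| True DGF prevalence | DGF subgroup, specificity 0.90 vs 0.98 | No-DGF subgroup, sensitivity 0.5 vs 0.9 | Equal labelling |
|---|---|---|---|
| 10% | −7.7 | +0.9 | 0 |
| 20% | −6.1 | +2.2 | 0 |
| 30% | −4.9 | +3.9 | 0 |

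**The case against.** Several points on the other side are sound.

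- **The overlap is limited.** An episode diagnosed as delayed graft function cannot be a tBPAR, so removing every rejection-form entry would discard usable DGF diagnoses. This stands, and the fix keeps that trigger.
- **The primary estimate is shielded.** The risk difference in SAP 4.7.1 is unadjusted. DGF reaches it through imputation of eGFR values expected to be few (2.5.3), in a model fitted by arm that already uses post-randomization eGFR, where such a predictor is legitimate. A reader might infer that the imputation biases the primary result. The documents do not show that.
- **Dialysis is no cure for timing.** A dialysis flag would also arise mostly after randomization, and local practice governs DGF treatment (Protocol 5.5.5). This stands, so the relabelling is needed whichever source is used.
- **No outside definition can be imposed.** A reader might conclude that DGF must mean dialysis within the first week. Neither document gives such a rule, and dialysis alone would miss slow function without dialysis.
- **Month 1 eGFR is also post-randomization** and is in the same logistic, ANCOVA and mixed models. True, so dropping DGF does not remove all such conditioning. But Month 1 eGFR is calculated from serum creatinine (SAP 4.5.1), not from the rejection form.
- **The subgroup is supportive** and lies outside the three-step testing hierarchy. This limits the consequence. It does not justify a subgroup partly defined by its outcome.

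A reader might also infer that the graft dysfunction term captures thrombosis, obstruction or drug toxicity. That depends on MedDRA coding that the documents do not set out, so it is not relied on here.

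**Conclusion.** The point holds on the text. DGF is derived without the dialysis data, one of its triggers can share an episode with tBPAR, and a variable observed mostly after open-label randomization is presented as baseline.

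The whole DGF group should not be read as enriched for rejection by construction. That applies only to patients entering through the reason-suspected trigger, and the documents do not give their number.

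The effect on the unadjusted primary risk difference is probably small. The DGF subgroup results, the pooling test and the adjusted eGFR models are more exposed. The shifts of 0.9 to 7.7 points rest on assumed prevalence, event rates and labelling differences between arms. Nothing in the documents shows that labelling did differ, and with equal labelling the shift is zero. The effect on the pooling test cannot be sized from the documents. The change should be made because it is cheap and removes an avoidable dependence on the outcome; the primary conclusion is not shown to be at risk.

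**What to change.** 1. In SAP 2.3.2, remove the trigger based on why rejection was suspected. Keep the adverse-event triggers and the form diagnosis of delayed graft function.
2. Add a DGF derivation from the Dialysis CRF, either as a further criterion or as a pre-specified sensitivity definition, with the early window chosen and stated by the sponsor. The extracted Table 6-1 appears to start the dialysis log at Day 4, so confirm that earlier sessions were recorded.
3. Move DGF out of the baseline list in SAP 2.2.1. Report it by arm as a post-randomization outcome and label its subgroup analyses as post-randomization.
4. Repeat the treatment-by-CNI logistic model, the eGFR ANCOVA and the mixed model without DGF as a sensitivity analysis. State in advance which version of the logistic model decides pooling.

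Cost: SAP wording, one derivation from data already collected, and three extra model runs. A small downside is that isolated early dialysis sessions given for other reasons may count as DGF.
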